16. SAFETY OUTCOMES

All safety analyses will be performed on the SAS.

16.1 Study Medication Exposure and Compliance

The following information on exposure and compliance to study medications will be reported:

- Treatment exposure (days): date of last dose of study medication – date of first dose of study medication + 1
- Total number of tablets taken: sum of all 'actual amount administered' during the study period
- Compliance (%): (total number of tablets taken / treatment exposure) x 100
- Status of a dose-up-titration at Week 6: Yes, No

Continuous variables will be summarized using number of patients without missing values, mean, standard deviation, median, 1st quartile, 3rd quartile, minimum, and maximum by treatment group and total. Categorical variables will be summarized using the total number of patients without missing values and the number and percentage of patients for each category by treatment group and total.

Document: Document path and title

Template No.: CCI

Reference: CCI

Effective Date: 15Oct2021

16.2 Adverse Events

The definition of AEs in the study protocol is restricted to the treatment-emergent adverse events (TEAEs) occurring after the first treatment exposure, while for this study AEs were collected from screening.

A TEAE is defined as AEs that first occurred or worsened in severity on or after the first administration of the study treatment during the treatment period.

TEAEs at 6 weeks will include TEAEs with the start date prior to 6 week (< Day 43) after the first administration of the study treatment. Imputation rules of partial/missing start/stop date on the AEs will be applied according to Appendix 1. Except for imputation of partial dates, no imputation will be done for missing values for all safety analyses.

A treatment-emergent serious adverse event (TESAE) and a treatment-related adverse event (TRAE) is identified by the response of 'Yes' on the Seriousness and Causality, respectively, on the AE page of eCRF. A TEAE leading to the premature discontinuation of the study is one with the response of 'Drug Withdrawn' on 'Action Taken with Study Drug' on the AE page of eCRF.

The number and percentage of patients experiencing at least one of TEAEs, TESAEs, TRAEs, and TEAEs leading to the premature discontinuation of the study at 6 weeks and 12 weeks will be presented by treatment group and tested using Chi-square test or Fisher's exact test as appropriate. The difference in the percentages will be presented with its corresponding 95% CI and p-value.

In addition, the numbers and percentages of patients experiencing at least one of TEAEs will be summarized by SOC and PT according to the MedDRA dictionary for each treatment group.

Individual TESAEs and TEAEs leading to the premature discontinuation of the study will be also listed with details including patient number, institution name, treatment group, sex, age, reported term, SOC, PT, start and stop date, severity, seriousness with criteria, causality, action taken and outcome.

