3.0 OBJECTIVES AND ENDPOINTS

Table 3-1 presents the objectives and corresponding endpoints of the study.

Table 3-1 Study objectives and endpoints

Objectives	Endpoints

Primary
 
 • To evaluate the effectiveness of early add-on of ezetimibe with atorvastatin in very high-risk patients. 	
 • Percentage change in LDL-C from baseline to week 6

Secondary
 
 • To evaluate the clinical effectiveness of early add-on of ezetimibe with atorvastatin in very high-risk patients. • To evaluate the safety of early add-on of ezetimibe with atorvastatin in very high-risk patients. 	
 • Proportion of patients achieving LDL-C goal of <55 mg/dL after 6 weeks and 12 weeks of treatment • Proportion of patients achieving LDL-C goal of <70 mg/dL after 6 weeks and 12 weeks of treatment • Percentage change in LDL-C from baseline to week 12 • Percentage change in HDL-C, non-HDL-C, triglycerides, and total cholesterol from baseline to week 6 and week 12 • Treatment-emergent adverse events (TEAEs) at 6 weeks and 12 weeks • Dropout rate due to TEAEs at 6 weeks and 12 weeks

Abbreviations: LDL-C=Low-density lipoprotein cholesterol; HDL-C= High-density lipoprotein cholesterol

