7.1 Discontinuation of Study Intervention

It may be necessary for a participant to permanently discontinue study intervention. If study intervention is permanently discontinued, the participant will remain in the study to be evaluated for lipid profile. See the SoA in Section 1.3 for data to be collected at the time of discontinuation of study intervention and follow-up and for any further evaluations that need to be completed.

The following criteria should be considered for discontinuation:

- Protocol deviation
- Lost to follow-up
- AST or ALT level $> 3 \times \text{ULN}$ for 2 consecutive times
- CK $> 10 \times \text{ULN}$ for 2 consecutive times
- Pregnancy
- Termination of the study by the investigator or Sponsor
- Difficult to continue the study according to the judgment of the investigator
- Adverse event
- Withdrew informed consent

If a participant who does not meet enrollment criteria is inadvertently enrolled, that participant must be discontinued from study intervention and the Sponsor or designee, must be contacted. An exception may be granted in rare circumstances for which there is a compelling safety reason to allow the participant to continue. In these rare cases, the investigator must obtain documented approval from the Sponsor or designee, to allow the participant to continue in the study.

Participants who discontinue study intervention will not be replaced.

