7.2 Participant Discontinuation/Withdrawal from the Study

A participant may withdraw from the study at any time at his/her own request or may be withdrawn at any time at the discretion of the investigator for safety, behavioral, or compliance, positive COVID-19 test or suspected Severe acute respiratory syndrome coronavirus 2 (SARS-CoV-2) infection, or administrative reasons. This is expected to be uncommon.

At the time of discontinuing from the study, if possible, an early discontinuation visit should be conducted, as shown in the SoA (Section 1.3). See SoA for data to be collected at the time of study discontinuation and follow-up and for any further evaluations that need to be completed.

The participant will be permanently discontinued from the study intervention and the study at that time.

If the participant withdraws consent for disclosure of future information, the Sponsor may retain and continue to use any data collected before such a withdrawal of consent.

If a participant withdraws from the study, he/she may request destruction of any samples taken and not tested, and the investigator must document this in the study site study records.

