8.4.3 Follow-up of AEs and SAEs

After the initial AE/SAE report, the investigator is required to proactively follow each participant at subsequent visits/contacts. All AEs, SAEs, and other reportable events, including pregnancy complications/outcomes and exposure during breastfeeding will be followed. Further information on follow-up procedures is provided in Section 10.3. Also, the

investigator will make every attempt to follow all non-serious AEs that occur in eligible participants for outcome.

Investigators remain responsible for following up on final event outcomes and events that are serious, considered related to the study treatment or study procedures, or that caused the participant to discontinue the study treatment or withdraw from the study.

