9.3.5 Safety Analysis

All safety analyses will be performed on the SAS.

The number and percentage of patients experiencing TEAEs, treatment-emergent serious adverse events (TESAE)s, Treatment-related adverse events (TRAEs) and TEAEs leading to the premature discontinuation of the study at 6 weeks and 12 weeks will be presented by treatment group and tested using Chi-square test or Fisher's exact test as appropriate. The difference in the percentages will be presented with its corresponding 95% CI and p-value.

The numbers and percentages of patients experiencing TEAEs will be summarized by system organ class (SOC) and preferred term (PT) according to the MedDRA dictionary for each treatment group.

Individual TESAEs and TEAEs leading to the premature discontinuation of the study will be listed with details including reported term, SOC, PT, start and stop date, severity, seriousness with criteria, causality, action taken and outcome.

For continuous other variables such as weight and vital signs parameters, descriptive statistics will be presented for outcome of interest at each visit and for change from baseline by treatment group.

Individual clinically significant changes in 12-lead ECG will be listed.

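### The secondary endpoint on dropout due to TEAEs is counted from a drug-withdrawal field, so it misreports any patient for whom stopping the drug and leaving the study are not the same event

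*SAP*

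**What the plan says.** Protocol section 3.0 and SAP section 3 list the secondary safety endpoint "Dropout rate due to TEAEs at 6 weeks and 12 weeks". Protocol 9.3.5 turns it into an analysis: "TEAEs leading to the premature discontinuation of the study at 6 weeks and 12 weeks will be presented by treatment group". SAP 16.2 repeats that wording and then gives the derivation: "A TEAE leading to the premature discontinuation of the study is one with the response of 'Drug Withdrawn' on 'Action Taken with Study Drug", as recorded on the AE page of the eCRF. No study-exit field enters the definition.

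On timing, SAP 16.2 says "TEAEs at 6 weeks will include TEAEs with the start date prior to 6 week", with the cut at Day 43. It gives no other dating rule for the discontinuation row.

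The protocol treats stopping drug and leaving the study in separate sections. Section 7.1: "If study intervention is permanently discontinued, the participant will remain in the study to be evaluated for lipid profile". Section 7.2, on leaving the study: "The participant will be permanently discontinued from the study intervention and the study at that time". Section 8.4.3 names the two as alternatives when it refers to events that "caused the participant to discontinue the study treatment or withdraw from the study".

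Study exit has its own summary. SAP section 10 and Table 1 report early discontinuation from the study by reason, with adverse event as one reason and the AST/ALT and CK criteria as two others. Table 2 lists each patient who left, with date of last visit and reason. SAP 4.5 declares no change to the analysis from the protocol.

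**The concern.** The endpoint's name and the analysis wording are about leaving the study. The field that fills it is about the drug. Under Protocol 7.1 a patient can stop drug for a TEAE and still attend Visit 4, and SAP 16.2 would report that patient as a dropout. The reverse can also happen: a patient leaves because of a TEAE but the drug-action field holds some other response, and is not counted.

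The timing is a second, separate matter. The 6-week row asks when the AE began, not when the patient stopped drug or left.

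At stake is whether a named secondary safety endpoint, shown in Tables 147 and 148 with a between-arm difference, 95% CI and p-value, measures what its label says. Table 1 will also show a count of exits for adverse events, and the SAP does not explain how the two relate.

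**Working it through.** The documents state no expected rate of dropout due to TEAEs, so there is no planned figure to reproduce. The check is a comparison of definitions, followed by the size of one misclassified patient.

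**Step 1. What each source records**

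- Endpoint (Protocol 3.0, SAP 3): dropout due to TEAEs.
- Analysis wording (Protocol 9.3.5, SAP 16.2): TEAE leading to discontinuation of the study.
- Derivation (SAP 16.2): drug action on the AE page equals Drug Withdrawn.
- Disposition (SAP 10, Tables 1 and 2): discontinuation from the study, with reason.

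**Step 2. The possible cases for a patient with a TEAE**

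| Drug action recorded | Study status | Counted by SAP 16.2 | Left the study for the TEAE |
|---|---|---|---|
| Drug Withdrawn | leaves for the TEAE | yes | yes |
| Drug Withdrawn | stays, as in Protocol 7.1 | yes | no (overcount) |
| another response | leaves for the TEAE | no | yes (undercount) |
| another response | stays | no | no |

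The rule is right in the first and last rows and wrong in the middle two.

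**Step 3. Size per patient**

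The denominator in Tables 147 and 148 is the safety set. Protocol 9.5 plans 63 randomized per group; assume all are treated. One patient = 100/63 = 1.59 percentage points. Protocol Appendix 6 allows up to 10% more enrolment: 126 × 1.10 = 138.6, so at most 138 patients, or 69 per arm, and one patient = 100/69 = 1.45 points.

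**Step 4. Range for the overcount, with assumed counts (63 per arm)**

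SAP rate = 100 × k/63, where k is the number with Drug Withdrawn for a TEAE. Study-dropout rate = 100 × k(1 − s)/63, where s is the share who stay.

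| k | SAP rate | s = 0 | s = 0.5 | s = 1 |
|---|---|---|---|---|
| 2 | 3.17% | 3.17% | 1.59% | 0% |
| 4 | 6.35% | 6.35% | 3.17% | 0% |
| 6 | 9.52% | 9.52% | 4.76% | 0% |

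Both k and s are assumptions; the documents give neither. Each patient missed in the other direction would raise the true rate above the SAP rate by the same 1.59 points.

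**Step 5. Timing**

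Take a TEAE that starts on Day 30 in a patient who leaves on Day 70. Onset is before Day 43, so the patient enters the 6-week discontinuation row although still in the study at Week 6. SAP Appendix 1 also assigns an AE with both dates missing to the 6-week set. The SAP gives no separate 12-week cut, so I read Table 148 as cumulative. On that reading the Day 30/Day 70 patient is in the 12-week count under either dating rule.

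**The case against.** Several points on the other side are sound.

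- **The two events may largely coincide.** Protocol 7.1's list of reasons for stopping study intervention includes study-level ones such as loss to follow-up and withdrawn consent. SAP Table 1 uses nearly the same list for leaving the study, and the protocol's schedule has a single early-discontinuation column. The protocol therefore blurs the distinction itself, and dropout is nowhere defined. A reader might infer that the dropout rate will certainly be wrong; the documents do not support that. If every drug stop for a TEAE is also a study exit, and the reverse, the cumulative count is right. What stands is that a drug-stop reading conflicts with the words *of the study* in Protocol 9.3.5 and SAP 16.2, and that 7.1 expressly keeps such patients in.
- **Onset dating is a defensible way to place a TEAE.** That holds for the TEAE rows as such. It fits less well for a row meant to show dropout by 6 weeks. A reader might also infer that onset dating is what brings patients who stay into the count. It is not: the drug-action field does that, and onset dating only moves patients into the 6-week count.
- **A difference between Table 1 and Tables 147/148 would not prove an error.** Table 1 covers randomized patients and the AE tables cover the safety set. Table 1 also spreads safety-related exits over several reasons. The exit count for adverse events stays visible there, so the information is not lost.
- **Inference is limited.** The p-value might suggest that a formal conclusion is at risk. SAP 8.2 restricts inferential conclusions to the primary endpoint.

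**Conclusion.** The mismatch of definitions is certain; its numerical consequence is conditional. As written, SAP 16.2 overcounts dropout for a patient who stops drug for a TEAE and stays, and undercounts it for a patient who leaves for a TEAE with another drug action recorded. Each such patient shifts the arm's rate by about 1.6 points, assuming 63 treated per arm. Because the share who stay is not given, neither the size nor the direction of the net error can be stated in advance.

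The onset rule separately inflates the 6-week count for patients with early onset and later exit, and leaves the cumulative 12-week count unchanged.

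The effect is on how one secondary safety endpoint is reported. The primary endpoint, its analysis and the sample size do not depend on it. It should be corrected before the tables are produced.

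**What to change.** In SAP 16.2 and Tables 147 and 148, replace the single discontinuation row with two:

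1. **Dropout due to TEAE.** Derive it from the study-discontinuation record. Count safety-set patients whose exit reason is adverse event, or one of the separately listed AST/ALT or CK reasons where that finding is also recorded as a TEAE. Link each exit to a treatment-emergent event, since AEs are collected from screening. Assign to 6 or 12 weeks by study-exit date. Using the adverse-event reason alone would miss the laboratory-based exits.
2. **TEAE leading to study-drug withdrawal.** Keep the present Drug Withdrawn derivation, relabelled, and assign it by last-dose date.

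Table 151 is a listing, so add a flag there showing which of the two applies to each event.

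Reconcile Protocol 7.1 and 9.3.5 with SAP 10 and 16.2, so that stopping drug and leaving the study are named consistently.

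The cost is SAP wording, one extra table row, one listing flag and a link between the AE and disposition data. The SAP already uses exit reason and timing (section 10) and date of last dose (section 16.1), so no new data collection appears to be needed.

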16.3 Vital Signs

The following vital sign parameters will be reported:

- Weight (kg)

Document: Document path and title

Template No.: CCI [REDACTED]

Reference: CCI [REDACTED]

Effective Date: 15Oct2021

- Systolic blood pressure (SBP) (mmHg)
- Diastolic blood pressure (DBP) (mmHg)
- Heart rate (Beat/min)

Each parameter at each visit and its change from baseline will be summarized using number of patients without missing values, mean, standard deviation, median, 1st quartile, 3rd quartile, minimum, and maximum by treatment group.

16.4 Laboratory tests

The following hematology, clinical chemistry and urinalysis parameters will be reported:

- Hematology: Platelet count, Red blood cell count, Total white blood cell (WBC), Hemoglobin, Hematocrit, Neutrophils, Lymphocytes, Monocytes, Eosinophils, Basophils
- Clinical chemistry: Blood urea nitrogen (BUN), Creatinine, Glucose, HbA1c, Gamma glutamyl transferase (GGT), Potassium, Sodium, Calcium, Albumin, Lactate Dehydrogenase (LDH), Uric acid, AST, ALT, Alkaline phosphatase (ALP), CK, Chloride, Total bilirubin, Direct bilirubin, Total protein, Phosphate, C-reactive protein
- Urinalysis: pH, Specific Gravity, Leucocytes, Protein, Bilirubin, Urobilinogen, Ketones, Red blood cells, Nitrite, Glucose

For quantitative laboratory tests, each parameter at each visit and its change from baseline will be summarized using number of patients without missing values, mean, standard deviation, median, 1st quartile, 3rd quartile, minimum, and maximum by treatment group.

A listing of patients with clinically significant changes in each parameter from baseline will be presented including patient number, institution name, treatment group, sex, age, visit, assessment date, parameter, observed value, baseline value, and normal range.

16.5 12-lead ECG

A listing of patients with clinically significant changes in 12-lead ECG from baseline will be presented including patient number, institution name, treatment group, sex, age, visit, date of 12-lead ECG, PR intervals, QRS intervals, QT intervals, QTc intervals, baseline value and normal range.

Document: Document path and title

Template No.: CCI

Reference: CCI

Effective Date: 15Oct2021

17. REFERENCES

Not applicable.

Document: Document path and title

Template No.: CCI [REDACTED]

Reference: CCI [REDACTED]

Effective Date: 15Oct2021

17.1 APPENDIX 1. Partial Date Conventions

Imputed dates will NOT be presented in the listings.

ALGORITHM FOR TREATMENT EMERGENCE OF ADVERSE EVENTS:

START DATE	STOP DATE	ACTION
Known	Known	
 The start date of AE < the first date of study treatment, Non-TEAEs
	Partial	
 the start date of AE \geq the first date of study treatment, TEAEs
	Missing	
(For TEAE at 6 weeks, the start date of AE \geq the first date of study treatment and the start date of AE < the first date of study treatment + 6 weeks)

Partial	Known	
In case of missing or unknown month and day of the start date of AE,
 
 The year of the start date of AE < the year of the first date of study treatment, Non-TEAEs; The year of the start date of AE = the year of the first date of study treatment and the stop date of AE < the first date of study treatment, Non-TEAEs; The year of the start date of AE = the year of the first date of study treatment and the stop date of AE \geq the first date of study treatment, TEAEs; The year of the start date of AE > the year of the first date of study treatment, TEAEs; 
(For TEAEs at week 6, the year of the start date of AE > the year of the first date of study)

Document: Document path and title

Template No.: CCI

Reference: CCI

Effective Date: 15Oct2021

START DATE	STOP DATE	ACTION
		
treatment and the month and day of the first date of study treatment \geq 21st Nov)
 
In case of missing or unknown day of the start date of AE,
 
 • The year and month of the start date of AE < the year and month of the first date of study treatment, Non-TEAEs; • The year and month of the start date of AE = the year and month of the first date of study treatment and the stop date of AE < the first date of study treatment, Non-TEAEs; • The year and month of the start date of AE = the year and month of the first date of study treatment and the stop date of AE \geq the first date of study treatment, TEAEs; • The year and month of the start date of AE > the year and month of the first date of study treatment, TEAEs 
(For TEAEs at week 6, the year and month of start date \leq the year and month of the first date of study treatment + 6 weeks)

	Partial	Missing or unknown month and day of the stop date of AE will be replaced by 31st Dec. Missing or unknown day of the stop date of AE will be replaced by the last day of the month.

 Document: Document path and title

Template No.: CCI [REDACTED]

Reference: CCI [REDACTED]

Effective Date: 15Oct2021

START DATE	STOP DATE	ACTION
		
In case of missing or unknown month and day of the start date of AE,
 
 • The year of the start date of AE < the year of the first date of study treatment, Non-TEAEs; • The year of the start date of AE = the year of the first date of study treatment and the stop date < the first date of study treatment, Non-TEAEs; • The year of the start date of AE = the year of the first date of study treatment and the stop date \geq the first date of study treatment, TEAEs; • The year of the start date of AE > the year of the first date of study treatment, TEAEs 
(For TEAEs at 6 weeks, the year of the start date of AE > the year of the first date of study treatment and the month and day of the first date of study treatment \geq 21st Nov)
 
In case of missing or unknown day of the start date of AE,
 
 • The year and month of the start date of AE < the year and month of the first date of study treatment, Non-TEAEs; • The year and month of the start date of AE = the year and month of the first date of study treatment and the stop date < the first date of study treatment, Non-TEAEs;

 Document: Document path and title

Template No.: CCI

Reference: CCI

Effective Date: 15Oct2021

START DATE	STOP DATE	ACTION
		
 The year and month of the start date of AE = the year and month of the first date of study treatment and the stop date \geq the first date of study treatment, TEAEs The year and month of the start date of AE $>$ the year and month of the first date of study treatment, TEAEs (For TEAEs at 6 weeks, the year and month of start date \leq the year and month of the first date of study treatment + 6 weeks)
	Missing	
In case of missing or unknown month and day of the start date of AE,
 
 The year of the start date of AE $<$ the year of the first date of study treatment, Non-TEAEs; the year of the start date of AE \geq the year of the first date of study treatment, TEAEs (For TEAEs at 6 weeks, the year of the start date of AE = the year of the first date of study or the year of the start date of AE $>$ the year of the first date of study treatment and the month and day of the first date of study treatment \geq 21st Nov) 
In case of missing or unknown day of the start date of AE,
 
 The year and month of the start date of AE $<$ the year and month of the first date of study treatment, Non-TEAEs;

Document: Document path and title

Template No.: CCI

Reference: CCI

Effective Date: 15Oct2021

START DATE	STOP DATE	ACTION
		
 The year and month of the start date of AE \geq the year and month of the first date of study treatment, TEAEs 
(For TEAEs at 6 weeks, the year and month of start date \leq the year and month of the first date of study treatment + 6 weeks)

Missing	Known	
 The stop date of AE $<$ the first date of study treatment, Non-TEAEs; The stop date of AE \geq the first date of study treatment, TEAEs and TEAEs at 6 weeks
	Partial	
Missing or unknown month and day of the stop date of AE will be replaced by 31st Dec. Missing or unknown day of the stop date of AE will be replaced by the last day of the month.
 
 The stop date of AE $<$ the first date of study treatment, Non-TEAEs; The stop date of AE \geq the first date of study treatment, TEAEs and TEAEs at 6 weeks
	Missing	TEAEs as well as TEAEs at 6 weeks

 Document: Document path and title

Template No.: CCI [REDACTED]

Reference: CCI [REDACTED]

Effective Date: 15Oct2021

ALGORITHM FOR PRIOR/ CONCOMITANT MEDICATIONS/ PROCEDURES:

START DATE	STOP DATE	ACTION
Will not imputed	Known	If the stop date of medications/procedures < the first date of study treatment, assign as prior; If the stop date of medications/procedures \geq the first date of study treatment or if ongoing is checked, assign as concomitant
	Partial	Impute the stop date of medications/procedures as the latest possible date (i.e. last day of month if day unknown or 31 st December if day and month are unknown), then: If the stop date of medications/procedures < the first date of study treatment, assign as prior; If the stop date of medications/procedures \geq the first date of study treatment or ongoing is checked, assign as concomitant
	Missing	Assign as concomitant

 Document: Document path and title

Template No.: CCI [REDACTED]

Reference: CCI [REDACTED]

Effective Date: 15Oct2021

